21.3 SLIT LAMP EXAM

Masked assessment: This assessment should be performed by the masked assessor.

A standard slit-lamp examination shall be performed including inspection of the cornea at a magnification of 10X and/or 16X for the presence or active inflammation or structural change, the iris and anterior chamber for inflammation, and the eyelids for crusts, collarettes, or scales.

21.4 TEAR BREAKUP TIME (TBUT)

Masked assessment: This assessment should be performed by the masked assessor.

Preparation of Fluorescein Solution Per the Gyau Method⁴⁷

1. Obtain a tube with the pre-cut Fluorescein strips prepared per the instructions provided in Appendix C. Make sure the pieces of the strips are lying at the bottom part of the tube.
2. Pipette 200µL of sterile saline into the tube containing the cut strips. Gently shake the tube to make sure the fluid is covering all the pieces of the cut strips and cover with the lid.

3. Wait 3-15 minutes before using the fluorescein solution.

⁴⁷ Gyau DA, Begley CF, Nelson JD. A simple cost effective method for preparing FL and LG solutions. Ocular Surface. 2018;16:139-145.

Measuring Tear Break-Up Time

1. Using a micropipette, instill 5 μ L of the fluorescein solution into the lower conjunctival fornix.
2. Measure TBUT quickly after instilling the fluorescein.
3. Use the cobalt blue illumination of the slit lamp and a Wratten filter.
4. Ask the subject to blink 3 times and then hold their eye open (e.g., “Blink, blink, blink, hold”).
5. Using a stopwatch, record the time when the tear film breaks-up.
6. Repeat the test 3 times per eye and take the average of the 3 measurements.
7. Discard the remaining fluorescein solution and microcentrifuge tube.

Tips for Tear Break-up Time

- TBUT is the number of seconds between a blink and the appearance of a first dry spot or negative staining in the tear film.
- TBUT measurements should be done quickly after installation of the dye because, in the presence of epithelial defects, the fluorescein will diffuse into the tissue and the borders of staining become indistinct, as does the intensity of staining of both tear film and cornea.
- Clear instructions should be provided to subjects about the blink and hold sequence
- Clear instructions should be provided to the study staff about when to start the stop watch

21.5 CORNEAL STAINING

[figure not shown]
Masked assessment: This assessment should be performed by the masked assessor.

Measuring Corneal staining

1. Measure corneal staining within 1-4 minutes of installation of fluorescein dye to assure the dye does not diffuse into stroma, blurring the discrete margin of any staining defects.
2. Use moderate illumination on the slit-lamp and use cobalt blue filter on with yellow Wratten filter to improve any visualization of corneal staining. Use 3 mm width and 10x magnification for assessing corneal staining. .
3. Grade the corneal staining using the NEI/Industry Grading System provided in Figure 4 below.⁴⁸

Figure 4: NEI/Industry Grading System for Corneal Staining

Score each of 5 areas of the cornea and total score:

Grade 0: No staining
Grade 1: Scattered, micropunctate staining
Grade 2: Grouped, micropunctate staining
Grade 3: Diffuse micropunctate or macropunctate staining

Tips for Corneal Staining

- Ask subjects to blink several times to assure the uniform distribution of dye in cul-de-sac
- Make sure to use moderate illumination to avoid hyper reflection from the spots of fluorescein uptake

⁴⁸ Lemp MA. Report of the National Eye Institute/Industry workshop on Clinical Trials in Dry Eyes. CLAO J 1995;21: 221-232.

21.6 CONJUNCTIVAL STAINING

Masked assessment: This assessment should be performed by the masked assessor.

Preparation of Lissamine Green Solution Per the Gyau Method⁴⁹

1. Obtain a tube with the pre-cut lissamine green strips prepared per the instructions provided in Appendix C. Make sure the pieces of the strips are lying at the bottom part of the tube.
2. Pipette 200µL of sterile saline into the tube containing the cut strips. Gently shake the tube to make sure the fluid is covering all the pieces of the cut strips and cover with the lid.

3. Wait 5-15 minutes before using the lissamine green solution.

[figure not shown]
Grading Conjunctival Staining

1. Instill 5µL of lissamine green solution into the lower conjunctival fornix.
2. Wait at least 1 minute before grading the conjunctival staining. Perform grading within 4 minutes of instilling the solution.
3. Start with a low illumination and increase the level until the lissamine green staining is most visible.
4. Grade the conjunctival staining on moderate illumination per the NEI grading system shown below in Figure 5.
5. After use, discard the remaining solution and microcentrifuge tube.

⁴⁹ Gyau DA, Begley CF, Nelson JD. A simple cost effective method for preparing FL and LG solutions. Ocular Surface. 2018;16:139-145.

Figure 5: NEI/Industry Grading System for Conjunctival Staining

Score each of 6 areas of the conjunctiva and total score:

Grade 0: No staining

Grade 1: Scattered, micropunctate staining

Grade 2: Grouped, micropunctate staining

Grade 3: Diffuse micropunctate or macropunctate staining

Tips for Conjunctival Staining

- Ask subjects to blink several times to assure the uniform distribution of dye in cul-de-sac
- Make sure to identify pooling or a stained mucus strand. Ask subjects to blink a couple of times when in doubt.

21.7 SCHIRMER 1 TEST

The Schirmer 1 Test measures aqueous tear quantity and is an indication of aqueous-deficient dry eye. The Schirmer 1 test, without anesthesia, should be performed by placing the filter strip in the inferior fornix for 5 minutes. Remove the strips and measure wetting in millimeters.

21.8 MEIBOMIAN GLAND SECRETION SCORING

Masked assessment: This assessment should be performed by the masked assessor.

The Meibomian Gland Secretion Scoring is an assessment of the quality of the secretions produced by the meibomian glands in the lower eyelids. The Meibomian Gland Secretion Scoring should be performed using the Meibomian Gland Evaluator (TearScience, Inc.). Ensure that the instrument has been cleaned using alcohol prior to each use.

Grade the quality of secretions in the lateral, central and temporal thirds of the lower eyelids. Grade the 5 central glands in each region, for a total of 15 glands per eye.

Per the method described by Korb et al,⁵⁰ place the part of the instrument's contact surface onto the skin immediately inferior to the eyelashes of the lower eyelid so that the long dimension is parallel to the eyelid margin. Once full contact is achieved between the instrument and the skin immediately below the lash line of the lower lid, rotate the shaft of the instrument downward approximately 15 to 45 degrees. Then, depress the shaft midway (~3mm) and roll the lower eyelid margin slightly outward. Make sure to avoid contact with the ocular surface.

Hold the instrument in place over each third of the lid for a minimum of 10 and a maximum of 15 seconds while grading the quality of secretion of the 5 glands in the center of the instrument (15 glands total per eye). Grade the quality of the secretions per the following scale described by Lane et al⁵¹:

- 0 = nothing
- 1 = toothpaste
- 2 = cloudy
- 3 = clear

From this assessment the following endpoints will be calculated:

- Total Meibomian Gland Secretion Score: Sum of the grade (0 – 3) for each of the 15 glands. Range for this score is 0-45.
- Count of the number of Meibomian glands yielding clear liquid secretions. Range for this count is 0-15.
- Count of the number of glands secreting any liquid (clear or cloudy). Range for this count is 0-15.

21.9 INTRAOCULAR PRESSURE

Masked assessment: This assessment should be performed by the masked assessor.

The same method of measuring intraocular pressure should be used at each visit. Intraocular pressure should be measured with applanation tonometry (e.g. Goldmann tonometer, if available).

⁵⁰ Korb DR, Blackie CA. Meibomian gland diagnostic expressibility: correlation with dry eye symptoms and gland location. *Cornea*. 2008;27: 1142–1147.

⁵¹ Lane SS, DuBiner H, Epstein RJ, et al; A New System, the LipiFlow, for the Treatment of Meibomian Gland Dysfunction. *Cornea*. 2012; 31 : 396-404.

21.10 QUESTIONNAIRES

21.10.1 GENERAL INSTRUCTIONS FOR QUESTIONNAIRES

The subject should complete all required questionnaires at the beginning of each visit before conducting other clinical testing. The only exception to this guideline is the Discomfort/Pain Questionnaire administered on Day 0, which is completed by the subject just following the study treatment (refer to instructions provided in Sections 9.5.4 and 9.5.5).

Provide a paper copy of the questionnaires and a blue or black ink pen to the subject. Review the instructions for each questionnaire with the subject and answer any questions they have about how to complete them. Then allow the subject to complete the questionnaires on their own (i.e. self-administered) without any assistance.

Study staff should review the questionnaires before the subject leaves the office to check for missing or multiple answers on a given question. If these are found, please point this out to the subject and allow them to revise their response(s) to the specific question(s). Please confirm initials and date of the subject on the last page of the questionnaire. Do not allow the subject to take the questionnaires home.

21.10.2 OSDI QUESTIONNAIRE

The OSDI has 12 questions. Based on the answers provided by the subject, study staff calculate the overall OSDI Total score (from 0-100) and scores for the three subscales according to the OSDI instructions. Based on the recommended cutoffs for OSDI Total score, the severity of the subject's dry eye symptoms will be categorized as follows:

- Normal – 0-12
- Mild – 13-22
- Moderate – 23-32
- Severe – 33 or higher

21.10.3 SANDE QUESTIONNAIRE AND EYE DRYNESS VAS

The SANDE is a simple dry eye instrument containing two items measuring the frequency and severity of symptoms, each is assessed on a 100 mm visual analog scale (VAS) ranging from 'Never/Very comfortable' to 'All the time/Very severe' and scored from 0 to 100. The Eye Dryness Visual Analog Scale measures subject's level of discomfort related to eye dryness ranging from "No discomfort/maximal discomfort."

Three scores will be obtained from the SANDE:

- Frequency score (ranging from 0 to 100): The distance (in mm) between the left end of the scale and the subject's response.
- Severity score (ranging from 0 to 100): The distance (in mm) between the left end of the scale and the subject's response.
- A SANDE Total score (also ranging from 0 to 100): This is calculated as the square-root of the product of the Frequency and Severity scores.

The Eye Dryness Score is derived from the Eye Dryness Visual Analog Scale. The Eye Dryness Score (ranging from 0 to 100) is the distance (in mm) between the left end of the scale and the subject's response.

Study staff should instruct subjects to record their response to each question by placing a vertical line (not an "X") across the horizontal line of the visual analog scale.

21.10.4 DISCOMFORT/PAIN QUESTIONNAIRE

The Discomfort/Pain Questionnaire is designed to assess the degree of discomfort or pain that the subject experiences during and immediately after the study treatment on Day 0 and post-treatment (Day 1). Subjects are asked to indicate their level of discomfort and pain using a Visual Analog Scale provided in the case report forms.

22 APPENDIX B – STATISTICAL ANALYSIS PLAN

22.1 EFFECTIVENESS ENDPOINTS AND ANALYSIS METHODS

22.1.1 PRIMARY EFFECTIVENESS ENDPOINT

The primary effectiveness endpoints are the change from baseline in Tear Break-Up Time (TBUT) and the total Meibomian gland secretion score (MEIB) at the 1 month follow up. Change is calculated as: 1 month – baseline, so a positive change is better. Both endpoints will be analyzed using a linear mixed effects (LME) model. This will allow for the proper incorporation of within-person correlation into the statistical tests, and will also allow for adjustment for baseline measurements. Both of these should increase the power over the simple “t-test using one eye” approach.

Since the SmartLid device was modified during the trial, all effectiveness analyses will be carried out with the Cohort 2 subjects only (i.e. subjects enrolled after the modified device was introduced). The primary effectiveness outcomes of the Cohort 1 subjects will be summarized separately by descriptive statistics (mean, median, standard deviation, minimum, and maximum).

The linear mixed effects model for TBUT can be written as follows:

$$y_{ij} = \beta_0 + \beta_1 T_i + \beta_2 TBUT_{ij,0} + b_{0i} + \epsilon_{ij}$$

Where

- $TBUT_{ij,k}$ is the TBUT value for subject i , eye j , week k .
- y_{ij} is the 1 month change from baseline TBUT for subject i , eye j .
$$y_{ij} = TBUT_{ij,4} - TBUT_{ij,0}$$
- T_i is the binary treatment indicator for subject i (0 = LipiFlow, 1 = TearCare)
- β_0, β_1 , and β_2 are the fixed effect parameters:
 - β_0 is the mean change from baseline for the LipiFlow arm,
 - β_1 is the difference between TearCare and LipiFlow in mean change from baseline,
 - β_2 is the effect of each unit change in baseline TBUT.
- b_{0i} is the random effect (random intercept term) for subject i
$$b_{0i} \sim N(0, \sigma_a^2)$$
- ϵ_{ij} is the normally-distributed error term
$$\epsilon_{ij} \sim N(0, \sigma_e^2)$$
- $\{b_{0i}\}$ and $\{\epsilon_{ij}\}$ are independent

To demonstrate non-inferiority of the TearCare treatment to the LipiFlow control for TBUT we will test the null hypothesis that β_1 is less than the non-inferiority margin of 3 seconds:

$$H_0: \beta_1 \leq -3.0$$

$$H_A: \beta_1 > -3.0$$

That is, we seek to reject the non-inferiority null hypothesis that the TearCare change in TBUT is more than 3 seconds worse than the LipiFlow change in TBUT.

For this model there are several equivalent ways to carry out this test:

- Using our estimates of β_1 and its standard error, carry out a t-test for the hypothesis.
- Form a confidence interval for β_1 and show that the lower bound is above -3.0 seconds,
- Calculate the least squares mean (LSM) at the mean baseline TBUT for the contrast between treatment and control, and its associated confidence interval, and show that the lower bound is above -3.0 seconds.

We will use the third (LSM) method since it provides the most flexibility, also allowing exploratory analyses examining the effects of other covariates, contrasts between groups, etc.

As is standard practice in non-inferiority studies, all tests will be carried out at a one-sided $\alpha = 0.05$ (or equivalently, using two-sided 90% confidence intervals).

The MEIB endpoint will use the same model and the same testing methods. To demonstrate non-inferiority of the TearCare treatment to the LipiFlow control for MEIB we will test the null hypothesis that β_1 is less than the non-inferiority margin of 5 units:

$$H_0: \beta_1 \leq -5.0$$

$$H_A: \beta_1 > -5.0$$

The study will be a success if the non-inferiority null hypothesis is rejected for both TBUT and MEIB. No alpha adjustments for multiplicity are necessary.

If the two non-inferiority nulls are rejected then each will be re-tested for superiority (that is, against 0.0 instead of the non-inferiority margin). If the TearCare device is superior to the LipiFlow control for either endpoint (or both) it will be declared superior for that endpoint (or both).

The linear mixed effects models can be fit in SAS or R as follows:

In SAS:

```
Proc Mixed data=TearCare method=ml;
  class SUBJ TRT;
  model TBUT_DIFF = TRT TBUT_BL / solution;
  random intercept / subject=SUBJ;
```

In R:

```
library(lme4)
fit.tbut <- lmer(TBUT.DIFF ~ TRT + TBUT.BL + (1|SUBJ) ,
  REML=FALSE, data=TearCare)
```

Note that since we are interested in testing the fixed effects, ML (maximum likelihood) versus REML (residual maximum likelihood) estimates are being used.

If the estimated between-subject variance $\hat{\sigma}_a^2$ is close to 0 we will repeat the analysis without the random intercept term (that is, as a standard ANCOVA without a random patient effect).

There are different options for calculating the standard errors/confidence intervals. Standard diagnostic tests and plots for outliers, normality of the errors, homogeneity of variances, and homogeneity of slopes will be provided. Based on prior data there is every reason to expect that the TBUT and MEIB errors will be approximately normally distributed. However, if residuals do not appear sufficiently normally distributed, we will calculate the confidence interval for β_1 using bootstrap methods.

If the ANCOVA model is unsatisfactory (e.g. linearity of change with respect to baseline is not supported, or the slopes are different) then we will test the primary hypotheses and compute the confidence interval for the difference in change from baseline between the two treatments based on a LME model without the baseline covariate (i.e. a t-test with adjustment for correlation).

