12.2 ANALYSIS POPULATIONS

The per-protocol analysis population includes all subjects who have at least one follow-up visit and have no major protocol deviations, including specifically no use of dry-eye medications (Xiidra, Restasis). The primary and secondary endpoint analysis will be performed based on the Cohort 2 per-protocol population.

The intent-to-treat (ITT) analysis population includes all subjects who are randomized to either arm, regardless of treatment received. As a sensitivity analysis, the primary and secondary endpoint analyses will also be carried out on the Cohort 2 ITT population as well.

The effectiveness outcomes for Cohort 1 subjects will be summarized descriptively based on the available data of the per-protocol population. The effectiveness data listings will be Cohort 1 subjects that are excluded from in the per-protocol population will be provided separately.

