12.5.3 PRIMARY EFFECTIVENESS HYPOTHESES

The primary study hypotheses will demonstrate non-inferiority of the TearCare treatment as compared to LipiFlow, for both Tear Break-Up Time (TBUT) and overall Meibomian gland score (MEIB) in the Cohort 2 subjects (after SmartLid modification). The full statistical model for the analyses is described in the SAP (Appendix B).

To demonstrate non-inferiority of the TearCare treatment to the LipiFlow control for TBUT we will test the null hypothesis that $\beta_{1,TBUT}$ is less than the non-inferiority margin of 3 seconds:

$$H_0: \beta_{1,TBUT} \leq -3.0$$
$$H_A: \beta_{1,TBUT} > -3.0$$

Where $\beta_{1,TBUT}$ represents the difference in change from baseline (1 month – baseline, so positive is better) between the TearCare treatment and the LipiFlow control. The hypothesis will be tested by constructing a confidence interval (least squares mean interval) for $\beta_{1,TBUT}$ as described in the SAP.

To demonstrate non-inferiority of the TearCare treatment to the LipiFlow control for MEIB we will test the null hypothesis that $\beta_{1,MEIB}$ is less than the non-inferiority margin of 5 units:

$$H_0: \beta_{1,MEIB} \leq -5.0$$
$$H_A: \beta_{1,MEIB} > -5.0$$

Where $\beta_{1,MEIB}$ represents the difference in change from baseline (1 month – baseline, so positive is better) between the TearCare treatment and the LipiFlow control for the overall Meibomian gland score. The hypothesis will be tested by constructing a confidence interval (least squares mean interval) for $\beta_{1,MEIB}$ as described in the SAP.

Both hypotheses will be tested at a one-sided $\alpha = 0.05$. As both hypotheses will need to be rejected for study success there is no multiplicity adjustment necessary.

If non-inferiority of the TearCare device is established as described above, then we will proceed to test for superiority for each of the two primary endpoints, that is, we will repeat the two hypothesis tests with non-inferiority margins set to 0. If either of the two superiority tests is rejected then the TearCare device will be declared superior for that endpoint.

The primary effectiveness outcomes of the Cohort 1 per-protocol population will be summarized separately by descriptive statistics for continuous variables such as mean, median, standard deviation, minimum, and maximum.

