12.5.6 SECONDARY EFFECTIVENESS ENDPOINTS

The secondary effectiveness endpoints include change from baseline for the following outcomes:

1. Ocular Surface Disease Index (OSDI) score
2. Corneal staining scores
3. Conjunctival staining scores
4. Symptom Assessment iN Dry Eye (SANDE) scores
5. Eye Dryness Score
6. Number of Meibomian Glands Yielding any liquid
7. Number of Meibomian Glands Yielding clear liquid

If both primary effectiveness hypotheses are both met for the Cohort 2 per-protocol population, then we will sequentially test each of the secondary effectiveness endpoints based on the Cohort 2 per-protocol population to determine whether there is a significant change between baseline and 1 month. In each case we will test the null hypothesis that the change is 0 against the appropriate alternative (depending on the favorable direction). All testing of the secondary endpoints will be done using a two-sided alpha of 0.05. We will test the secondary endpoints in the order listed, stopping at the point where a test fails to reject. This sequential procedure controls the overall type I error rate for the secondary endpoints.

The secondary endpoints can be divided into two groups, those which are measured on a per-eye basis (Corneal Staining, Conjunctival Staining, Meibomian gland scores) and those measured on a per-subject basis (OSDI Score, SANDE Scores, Eye Dryness Score).

The per-eye secondary endpoints (Corneal Staining, Conjunctival Staining, Meibomian gland counts) will be tested using a similar linear mixed effects modeling approach as for the primary endpoint, with treatment as a fixed effect, and including a random intercept per subject to account for correlation.

The per-subject secondary endpoints (OSDI score, SANDE scores, Eye Dryness Score) are measured at the subject level so there is only one measurement per subject. For these endpoints a paired t-test will be used to evaluate change from baseline to 1 month.

The secondary effectiveness outcomes of the Cohort 1 per-protocol population will be summarized separately by descriptive statistics (mean, median, standard deviation,

minimum, and maximum for the continuous variables; count and percent for the categorical outcomes).

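### Superiority over LipiFlow is tested at the non-inferiority level (one-sided 0.05, 90% CI) and in the per-protocol set, so it can be claimed at two-sided p < 0.10

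*Combined protocol and SAP*

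**What the plan says.** **Level.** SAP section 22.1.1 states "As is standard practice in non-inferiority studies, all tests will be carried out at a one-sided" alpha of 0.05, "or equivalently, using two-sided 90% confidence intervals". The only reason given is non-inferiority practice.

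**Superiority step.** Once both non-inferiority nulls are rejected, the same SAP section says "each will be re-tested for superiority (that is, against 0.0 instead of the non-inferiority margin". Protocol section 12.5.3 puts it as "we will repeat the two hypothesis tests with non-inferiority margins set to 0", and continues: "If either of the two superiority tests is rejected then the TearCare device will be declared superior for that endpoint". Neither section states a separate alpha or confidence level for this step.

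**Analysis set.** Protocol section 12.2: "The primary and secondary endpoint analysis will be performed based on the Cohort 2 per-protocol population". Section 12.5.2 repeats this for the two primary endpoints. ITT, meaning all randomised subjects, is a sensitivity analysis. Per-protocol membership requires at least one follow-up visit and no major deviation. Section 9.9 also removes subjects from the point at which they start Restasis, Xiidra or another dry eye treatment.

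**Elsewhere.** For the secondary endpoints, section 12.5.6 says "All testing of the secondary endpoints will be done using a two-sided alpha of 0.05".

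**The concern.** A one-sided 0.05 level with a per-protocol primary set is a choice the plan argues for in the non-inferiority setting. The superiority step takes over both features without an argument of its own. With the null at 0, a one-sided 0.05 test is a two-sided 0.10 test, so a claim that TearCare is better than an active device could rest on a 95% interval that includes no difference.

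The set matters for a different reason. Per-protocol membership depends on events after randomisation. Subjects know their arm (section 7), and starting another dry eye treatment may itself reflect a poor response. Exclusions could therefore differ between arms and be related to outcome. A superiority claim should keep the randomised comparison as its basis.

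This point is about the level and set of each single superiority test. It would apply if only one endpoint were tested.

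**Working it through.** **Inputs (SAP sections 22.3.1, 22.3.2 and 22.3.4).** TBUT: SD 6.0 s, margin 3.0 s, inflation factor for two eyes 1.4. MEIB: SD 9.0, margin 5.0, inflation factor 1.5. One-sided alpha 0.05, power 95% per endpoint, true difference 0, 69 subjects per arm, 10% loss.

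**Step 1: reproduce the plan's sample size.** Eyes per group = 2 × (1.645 + 1.645)² × SD² / margin².
- TBUT: 2 × 10.82 × 36 / 9 = 86.6, so 87; the t-based calculation gives 88, as stated. Then 176 × 1.4 = 246.4 eyes; / 0.9 = 273.8; / 2 = 136.9, so 137 subjects, as stated.
- MEIB: 2 × 10.82 × 81 / 25 = 70.1, so 71, as stated. Then 142 × 1.5 = 213; / 0.9 = 236.7; / 2 = 118.3, so 119, as stated.

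The design does run on one-sided 0.05, and only non-inferiority is powered.

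**Step 2: standard error at the planned size.** Analysed subjects per arm = 69 × 0.9 = 62.1, or 124.2 eyes. SE = SD × √(2 × inflation / eyes per arm).
- TBUT: 6 × √(2 × 1.4 / 124.2) = 0.901 s.
- MEIB: 9 × √(2 × 1.5 / 124.2) = 1.399 units.

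**Step 3: smallest observed advantage that earns a superiority claim.**

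| Endpoint | One-sided 0.05 (90% CI), 1.645 × SE | One-sided 0.025 (95% CI), 1.960 × SE |
|---|---|---|
| TBUT | 1.48 s | 1.77 s |
| MEIB | 2.30 units | 2.74 units |

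Using the estimated design effects of 1.36 and 1.44 instead of the inflated 1.4 and 1.5, 62 subjects per arm and t(122), the values are 1.47 against 1.76 s and 2.28 against 2.72 units. The conclusion is the same.

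**Step 4: what falls in the gap.** Take an observed TBUT advantage of 1.6 s. The 90% CI is 1.6 ± 1.48, or 0.12 to 3.08, and superiority is declared. The 95% CI is 1.6 ± 1.77, or −0.17 to 3.37. Here z = 1.6 / 0.901 = 1.78, two-sided p about 0.076.

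**Step 5: error rate per endpoint.** If the true difference is 0, the test alone gives 5%. Both non-inferiority tests must pass first. At the planned size their power is Φ(3 / 0.901 − 1.645) = 0.954 for TBUT and Φ(5 / 1.399 − 1.645) = 0.973 for MEIB. If the endpoints were independent and both true differences 0, the rates would be 0.05 × 0.973 = 4.9% for TBUT and 0.05 × 0.954 = 4.8% for MEIB. At one-sided 0.025 they would be 2.4% each. So 5% is an upper bound, and the gate hardly lowers it.

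**The case against.** **Superiority is not what the trial is for.** Section 2 says the objective is met by non-inferiority, success is rejection of both non-inferiority nulls, the proposed indication makes no comparison with LipiFlow, and the sample size assumes equal effects. All of this stands and limits the importance of the point. A reader might infer that the main result or overall study success is tested too loosely because of this step. The documents do not support that: testing non-inferiority and then superiority in fixed order needs no alpha split within an endpoint, and the superiority step cannot change the non-inferiority decision.

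**The level is inherited by wording.** The alpha sentence in section 12.5.3 refers to the two non-inferiority hypotheses. But the SAP says all tests, the superiority step is a repeat, and no other level appears. If another was intended, it still has to be written down.

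**The secondary endpoints are a weak comparator.** It is tempting to say that superiority gets twice the error allowed to a lower-ranked endpoint. Section 12.5.6, however, tests change from baseline to 1 month, not TearCare against LipiFlow, and it mentions a favourable direction alongside a two-sided alpha. It shows that the plan uses two-sided 0.05 elsewhere, and no more.

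**The ITT analysis is already planned, and assessors are masked (section 9.8).** Both are true. An ITT result will exist, but it will not govern the claim. Appendix B says only Cohort 2 subjects; the per-protocol restriction comes from sections 12.2 and 12.5.2. A reader might infer that the per-protocol rules favour TearCare by a definite amount. The documents give no exclusion rates by arm and no outcomes of excluded subjects. TBUT also has little room to fall from the pilot TearCare baseline means of 3.1 and 4.6 s. Neither direction nor size can be stated.

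**Naming ITT does not by itself bring back missing subjects.** This stands. The model needs a 1-month change, and section 22.1.3 details imputation for TBUT only. The fix must cover this.

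**Conclusion.** The point holds for the superiority step alone. As written, TearCare can be declared superior on an endpoint at two-sided p < 0.10 in the per-protocol set, at about 1.5 s or 2.3 units observed, where a 95% CI would need about 1.8 s or 2.7 units. The per-endpoint false-superiority rate is up to 5% instead of 2.5%.

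The thresholds rest on the plan's SDs, inflation factors and 10% loss. They ignore the gain from baseline adjustment and any further per-protocol exclusions, and they scale with the SD actually seen. The ratio between the two thresholds (1.645 / 1.960 = 0.84) does not depend on those inputs. That superiority should be held to a 95% CI in ITT is a matter of usual practice; the documents state no such requirement.

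The 5% figure is per endpoint. It should not be read as the chance of a false claim on either endpoint. The plan's reason for no adjustment, "As both hypotheses will need to be rejected for study success there is no multiplicity adjustment necessary", concerns the non-inferiority pair; sharing alpha across the two superiority tests is a separate question that this point does not settle.

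**What to change.** Limit the standard-practice sentence in SAP section 22.1.1 to the non-inferiority tests, and leave those tests as they are. In sections 12.5.3 and 22.1.1, replace the superiority wording with:

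> *TearCare is declared superior on an endpoint only if the lower limit of the two-sided 95% CI for TearCare minus LipiFlow exceeds 0 in the Cohort 2 ITT population, with missing 1-month TBUT and MEIB values handled by the multiple imputation of section 22.1.3 (extended to MEIB); the per-protocol result is supportive.*

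Extend section 22.1.3 accordingly. State there how subjects with neither a 2-week nor a 1-month value are imputed. This includes randomised subjects who withdraw before treatment, who may be replaced under section 9.10 but remain in ITT.

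The cost is SAP wording and an imputation model for MEIB. The 138 subjects and the non-inferiority power are unchanged. A superiority claim becomes slightly harder to make: at the planned size the observed advantage must be larger by about 0.3 s (1.77 − 1.48) or 0.4 units (2.74 − 2.30).
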